6.2.2 Weeks 1 to 6 - Intensive plasma exchange period

Full Plasma Exchange (Window range +/- 1 day)

Plasma samples will be collected from the subject before and 15-30 minutes after each procedure, to allow the pertinent tests. Additional plasma samples will be collected each time for storage at -70°C and possible future assays.

The following tests will be made before each procedure: biomarkers of AD (A β -40, A β -42, β -secretase, γ -secretase, cholesterol, LDL, HDL, VLDL, C-reactive protein, rheumatoid factor, IL-1b, IL-6, ferritin and TNF- α), coagulation factors (prothrombin time (Quick), aPPT, calcium and fibrinogen) and proteinogram (total proteins, albumin, α 1-globulina, α 2-globulina, β -globulina, γ -globulina and IgG). In addition, a cell count will be made including hematocrit, hemoglobin and erythrocytes, platelets and leukocytes (if an abnormal leukocyte count is recorded, it will be obligate to specify neutrophils, basophils, eosinophils, lymphocytes and monocytes). The samples obtained after plasma exchange will be used to evaluate the biomarkers of AD, cell count, platelets, coagulation factors (prothrombin time

(Quick), aPPT, calcium), proteinogram, fibrinogen and troponin, as well as other biochemistry parameters (AST, ALT, LDH and creatinine).

A maximum of six full plasma exchange sessions will be made during this period: one per week.

The subject will remain in the center throughout the procedure and then for as long as needed to ensure a safe return home, under conditions similar to before plasma exchange.

Before plasma exchange, a physical examination will be made, with the recording of any anomalies. Concomitant medication is also to be registered, together with any adverse event detected since the last visit or since the last plasma exchange session. The anxiety and restlessness tests, if necessary, will be performed before each plasma exchange process, and between 15-30 minutes after replacement. These tests will be carried out by the same patient supervisor.

Vital signs (axillary temperature, heart and respiration rate, and blood pressure) will be determined 15-30 minutes before replacement during and again 15-30 minutes after the procedure, and as often as considered opportune by the investigator.

Any adverse event during or after the procedure, will be recorded.

Control group

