6.2.4 Months 3 to 14 - Maintenance Period

Treatment Groups: Maintenance Period (Plasmaphereses + albumin or IVIG) (Window range +/- 5 days)

At months 6, 9, 12 and 14, the following cognitive impairment and behavioral tests will be made: ADAS-Cog, MMSE, NPS battery, ADCS-ADL, NPI, CDR-Sb, ADCS-CGIC, CSDD, CSSRS, QoL-AD and RUD-Lite[®]. Likewise, anxiety and restlessness tests will be made based on the Overt Aggression Scale (OAS) and the Agitated Behavior Scale (ABS), whenever considered opportune.

The plasma samples of the patient will be collected before and 15-30 minutes after each procedure, to allow the pertinent tests. These plasma samples collected before and after the procedure will be stored at -70°C for possible future assays.

The following tests will be made before each procedure: biomarkers of AD (A β -40, A β -42, β -secretase, γ -secretase, cholesterol, LDL, HDL, VLDL, C-reactive protein, rheumatoid factor, IL-1b, IL-6, ferritin, TNF- α), coagulation factors (prothrombin time (Quick), aPTT, calcium and fibrinogen), and proteinogram (total proteins, albumin, α_1 -globulina, α_2 -globulina, β -globulina, γ -globulina and IgG). In addition, a cell count will be made including hematocrit, hemoglobin and erythrocytes, platelets and leukocytes (if an abnormal leukocyte count is recorded, it will be obligate to specify neutrophils, basophils, eosinophils, lymphocytes and monocytes). The samples obtained after plasma exchange will only be used to evaluate the biomarkers of AD and, if necessary, to assess coagulation factors. A more intense monitoring is not considered mandatory since in this period the procedure is similar to a plasma donation plasmapheresis. However, the investigator can decide to assess other parameters for safety reasons. Other liver or kidney biochemical markers (AST, ALT, bilirubin, LDH, creatinine and troponin), and serology (anti-HIV and HCV antibodies, and HBsAg antigen) will be also done..

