If you are to use a central catheter for FPE you will receive a DVD with 4 short videos:

- 1) ***Simulated jugular central catheter implantation***
- 2) ***Sham procedures FPE + Albutein 5%, central access***
- 3) ***Sham procedures Low Volume Plasma Exchange (LVPE) + Albutein 20%***
- 4) ***Sham procedures LVPE + Flebogamma DIF 5%***

APPENDIX 10

HYPOVOLEMIA GUIDELINE

Recommendations for preventing hypotension related events in Low Volume Plasma Exchange procedures: Infusion of saline solution and adjustment of removed plasma volume in low-weight patients.

Date: 24SEP2014

Site: All Sites (Spain and US)

1. Infusion of saline solution

This recommendation is only applicable to the LVPE procedures with Albutein[®].

In LVPE with Albutein[®] infusion, a volume of 690-880ml of plasma is extracted during the procedure, depending on the patient's weight. However, based on the patient's weight and/or treatment arm, only a volume of 80-200ml of Albumin 20% is infused during the procedure. Due to the difference in volume, saline solution can be infused to reduce the risk of hypotension related events.

How to proceed for the LVPE with Albutein[®] infusion:

- 1- Perform plasma collection regularly
- 2- Infuse Albutein[®] regularly
- 3- Measure vital signs after infusion
- 4- Collect blood samples for laboratory tests
- 5- Infuse saline solution as recommended in table 1 (see below).
- 6- Measure vital signs after saline infusion

2. Adjustment of removed plasma volume in patients who weight less than 110 lbs.

This recommendation is applicable to ALL LVPE procedures (Albutein[®] and Flebogamma 5% DIF[®]).

In those patients whose weight is less than 110 lbs., the volume of plasma to remove will be proportional to the actual weight and calculated according to the following formula:

GRIFOLS

$$\text{Plasma volume to collect (mL)} = \frac{\text{Weight (lbs)} \times 690 \text{ mL}}{110 \text{ lbs}}$$

(see table 1 below as well).

For example, for a patient weighting 100 lbs:

$$\text{Plasma volume to collect (mL)} = \frac{100 \text{ lbs} \times 690 \text{ mL}}{110 \text{ lbs}} \approx 630 \text{ mL}$$

Table1. Removal and replacement volume during LVPE

| REMOVAL AND REPLACEMENT VOLUME DURING LVPE | | | | | |
|--|------------------------------|--|-------------------|---|---|
| Patient weight | Plasma collected | Albutein® to infuse depending on the treatment arm | | + | Saline Solution to infuse (arm 1, 2 &3) |
| | | Full dose (arm 1) | ½ dose (arm 2 &3) | | |

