	Version: Final 1.0 Effective Date: 31July2018
	Protocol Version: Version 5.0 Effective Date: Feb2018

If 2 or more assessments are falling into the range of a study visit, the assessment closest to the targeted study day will be used, if 2 assessments has the same distance to the targeted study day, the assessment after the targeted study day will be used for the summary statistics. The first Full Plasma Exchange Visit (Week1) will be used as reference for the slotting of all efficacy study visits, regardless of whether or not there is any deviation from the protocol regarding to the study treatment.

The biomarkers in plasma are assessed at each plasma exchange visit prior to the exchange (pre-exchange value) and after the plasma exchange (post-exchange value). The biomarkers in plasma will be slotted as follows:

- Baseline value is the last available value prior to treatment initiation (FPE1). If there is no available value prior to the treatment initiation, the pre-treatment value of FPE1 will be used as baseline value.
- No slotting will be applied to the pre- and post-exchange values of FPE1-FPE6, the intermediate visit, and LVPE1-LVPE12.
- If LVPE12 has been performed, the final visit will be analyzed as final visit. Otherwise, the values from the final visit will be slotted to the visit subsequent to the last performed plasma exchange and analyzed as pre-exchange value, e.g. if LVPE4 is the last performed plasma exchange, the value from the final visit will be analyzed as LVPE5 pre-exchange value.

No windowing schemas will be applied to the safety data (e.g. vital signs, laboratory values, etc.). For by-visit summaries, if there are multiple assessments at a post baseline visit then the last non-missing assessment at that visit will be used for the summary. This includes assessments at the scheduled and unscheduled visits.

Summaries of clinically significant abnormal values will include all post baseline values (including scheduled, unscheduled, and early termination visits).

Descriptive statistics for continuous variables include n, mean, standard deviation, standard error of the mean, median, minimum, and maximum. Descriptive statistics for categorical variables include patient counts and percentages.

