7.2 SAFETY END POINTS

The primary criterion of safety will be the percentage of plasma exchanges (full and low volume exchanges, including the infusion of albumin and IVIG) associated with at least one adverse event that may be related to the study procedure (adverse reactions). In addition, consideration globally will be made of the percentage plasma exchanges (full and low-volume exchanges, including the infusion of albumin and IVIG) involving some adverse event, whether or not related to the procedure.

Vital signs (blood pressure, heart rate, respiration rate, and body temperature) will be recorded before, during and after each plasma exchange session, where required. Evaluation will also be made (where required) of the different laboratory test parameters (blood cell counts, platelet count, prothrombin time (Quick), fibrinogen, total proteins, and calcium).

During the treatment periods (before each plasma exchange) and on the days when there is no replacement, anxiety and restlessness tests will be made based on the Overt

	Title: Statistical Analysis Plan
	Project #: IG1002 AMBAR
	Version: Final 1.0 Effective Date: 31July2018
	Protocol Version: Version 5.0 Effective Date: Feb2018

Aggression Scale (OAS) and the Agitated Behavior Scale (ABS), whenever considered opportune.

According to the criterion of the investigator, all the clinically important changes in vital function, laboratory test parameters and neuroimaging findings will be evaluated. Any adverse events occurring following start of treatment will be counted as treatment emergent.

The analysis of tolerability will be based on description of the safety variables according to their nature.

The adverse reactions will be coded according to the adverse events classification of the World Health Organization (WHO) (MedDRA current version), and will be described by a synonym (Preferred Term) and the affected organ / system, the intensity, causality and seriousness.

The safety population will be used for all safety summaries unless otherwise noted. Summaries will be presented by treatment group and overall unless otherwise noted.

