7.2.3 Vital Signs

Summary statistics for vital signs will be presented at baseline, each visit, and end point. Actual values and changes from baseline to each visit and end point will be summarized using descriptive statistics. The incidence of clinically significant abnormal values will be summarized for selected vital signs using descriptive statistics.

Criteria for Clinically Significant Vital Signs

Vital Sign	Criterion value	Change relative to baseline
Heart rate	≥120 bpm	Increase of ≥15
	≤50 bpm	Decrease of ≥15
Systolic blood pressure	≥180 mm Hg	Increase of ≥20
	≤90 mm Hg	Decrease of ≥20
Diastolic blood pressure	≥105 mm Hg	Increase of ≥15
	≤50 mm Hg	Decrease of ≥15
Body temperature	≥38.3°C	Change of ≥1.1°C

In order to be identified as clinically significant abnormal, a value would need to meet both conditions: have a value beyond the criterion value and a change of at least the magnitude specified in the change from baseline column.

A listing for clinically significant abnormal vital signs will be presented.

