7.2.4 Clinical Laboratory Tests

Summary statistics for biochemistry, proteinogram, hematology, and clotting laboratory tests will be presented at each visit. Actual values and changes from baseline to each visit will be summarized using descriptive statistics. All changes will be changes from the baseline value, there will be no comparisons in the values between the pre- and post FPE values. Maximal shifts from baseline during the FPE and during the LVPE will be summarized using the CTC AE grading system Version 4.03 and patient counts. Shifts for laboratory values which have no CTC AE grade will be based on the normal ranges (below, within, and above the normal range, if applicable).

	Title: Statistical Analysis Plan
	Project #: IG1002 AMBAR
	Version: Final 1.0 Effective Date: 31July2018
	Protocol Version: Version 5.0 Effective Date: Feb2018

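### Read as written, the SAP's by-visit safety rule keeps one value per visit regardless of scheduled time point, so the by-visit vital-sign and laboratory tables drop or mix before, during and after values

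*SAP*

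**What the plan says.** SAP section 7 applies no windowing to safety data, naming vital signs and laboratory values as examples. It then states, for by-visit summaries, that "if there are multiple assessments at a post baseline visit then the last non-missing assessment at that visit will be used for the summary". No scheduled time point within the visit is mentioned.

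The planned data have such time points:

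- **Vital signs.** SAP 7.2 says they "will be recorded before, during and after each plasma exchange session, where required". The Appendix 8 schedule marks all three at the exchange visits. SAP 7.2.3 plans the output by visit only: "Summary statistics for vital signs will be presented at baseline, each visit, and end point".
- **Laboratory tests, intensive phase.** Appendix 8 schedules eight rows both before and after each full plasma exchange (FPE): blood cell counts, platelets, prothrombin time, aPTT, fibrinogen, proteinogram, IgG and calcium. Five more rows are scheduled after only.
- **Laboratory tests, maintenance phase.** At each low-volume exchange (LVPE), four of those eight rows are before only (cell counts, platelets, fibrinogen, proteinogram). The other four (prothrombin time, aPTT, IgG, calcium) are mandatory before and optional after. Protocol 6.2.4 says of this phase: "The samples obtained after plasma exchange will only be used to evaluate the biomarkers of AD and, if necessary, to assess coagulation factors".

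SAP 7.2.4 adds that "there will be no comparisons in the values between the pre- and post FPE values". For plasma biomarkers, by contrast, SAP sections 7 and 7.3.1 keep the values before and after each exchange separate.

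**The concern.** A rule that takes the last value at a visit is sensible for unplanned repeats. Here each visit has planned, physiologically different time points, and the rule makes no distinction between a repeat and a planned later reading.

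Three things follow. By-visit vital-sign tables would show the reading after the session and not those before or during it. By-visit laboratory tables would change from post-exchange to mainly pre-exchange values at the same point where the trial moves from intensive to maintenance treatment, so time point and phase are confounded in the display. And in maintenance, four laboratory tests would be tabulated post-exchange in patients who had an optional sample and pre-exchange in the rest, which makes the mixture depend on clinical judgement.

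Changes in vital signs and laboratory findings are part of the stated safety objective. Protocol 5.2.2 names hypotension and dilution of coagulation factors among the risks of the procedure, so readers will look to these tables.

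**Working it through.** The plan gives no figure on this point to reproduce. The check is to apply the literal rule to the schedule and count what reaches a by-visit table for one patient who completes every session.

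**Inputs**

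- Full exchanges: 6. Protocol 6.2.2: "A maximum of six full plasma exchange sessions will be made during this period: one per week".
- Low-volume exchanges: 12, one per month (protocol 6.2.4).
- Vital-sign sets per exchange: 3 (SAP 7.2, Appendix 8).
- Laboratory rows with a pre-exchange sample: 8 at FPE visits and 8 at LVPE visits (Appendix 8).
- Baseline: the last value before the first exchange (SAP 7), so the FPE1 pre-exchange value can serve as baseline.

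**Vital signs**

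Scheduled: (6 + 12) × 3 = 54 sets.

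| | Before | During | After |
|---|---|---|---|
| Scheduled | 18 | 18 | 18 |
| Reaches a by-visit table | 1 (FPE1, as baseline) | 0 | 18 |
| Not tabulated by visit | 17 | 18 | 0 |

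Not tabulated: 17 + 18 = 35 of 54 (65%). This assumes that the after reading is present. If it is missing, the rule falls back to an earlier reading, and the by-visit row then mixes time points.

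**Laboratory tests, pre-exchange slots**

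Scheduled: 8 × 6 + 8 × 12 = 48 + 96 = 144.

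| Slots | Count | Fate under the rule |
|---|---|---|
| FPE1, 8 rows | 8 | Can serve as baseline |
| FPE2 to FPE6, 8 rows | 8 × 5 = 40 | Replaced by the post-exchange value |
| LVPE, 4 before-only rows | 4 × 12 = 48 | Kept; the only scheduled value |
| LVPE, 4 rows with optional after | 4 × 12 = 48 | Kept unless an optional sample was taken |

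The loss is at least 40/144 = 28%. At most it is (40 + 48)/144 = 88/144 = 61%, if every optional sample is taken.

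These counts follow Appendix 8. The text of protocol 6.2.4 lists fibrinogen among the coagulation factors and does not mention a post-exchange IgG, so the set of four mixed tests differs slightly between the two places.

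**Passages side by side**

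Earlier in SAP section 7, actual values and changes from baseline are promised at every time at which a variable is measured. That conflicts with one value per visit. The same section leaves pre- and post-exchange plasma biomarkers at their own time points, so the structure was recognised there but not carried over to safety.

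**The case against.** The best defence is that the literal reading is not what was meant. The general promise in SAP section 7 covers every measurement time. The sentence after the rule refers to scheduled and unscheduled visits, which suits a rule for repeats. SAP 7.2.4 mentions both pre- and post-FPE values, takes all changes from baseline, and declines only the within-session comparison, which presupposes that both are summarised. This has weight, but the last-value sentence is the specific instruction for by-visit safety summaries. At best the SAP contradicts itself and the tables depend on how a programmer reads it.

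It is also fair to say that extremes are reported elsewhere. Clinically significant vital signs draw on all post-baseline values, laboratory shifts are the maximal shift in each phase, and the primary safety criterion counts exchanges followed by a related adverse event within 72 hours. That stands, and it limits the consequence. It does not fully replace the by-visit view. A systolic value must be 90 mm Hg or lower and also at least 20 below study baseline to be flagged, so a fall from 150 to 95 would not appear there. A maximal shift does not show recovery before the next exchange.

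A reader might infer more than the documents support:

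- **That pre-exchange laboratory values vanish from every by-visit table.** They do not. At LVPE visits they are the only scheduled value for four rows and the only mandatory one for four more.
- **That any rise at LVPE1 would be an artefact.** LVPE1 is at week 9, three weeks after the sixth full exchange, so some recovery would be real. Proteinogram and IgG also have a sample at the intermediate visit. Post-exchange values are true measurements. The documents give no figure from which to size a step.
- **That the tabulated vital signs are post-saline readings.** Appendix 10 does include the step "Measure vital signs after saline infusion", but it is discretionary and limited to low-volume exchanges with albumin. Appendix 8 schedules no such reading, so the documents do not show that it enters the safety data.

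**Conclusion.** The point holds for the by-visit descriptive safety tables. As written, the rule leaves about 35 of 54 vital-sign sets and 40 to 88 of 144 pre-exchange laboratory slots out of those tables for a completer. It shifts the laboratory display from post-exchange to mainly pre-exchange between phases, and it mixes time points for prothrombin time, aPTT, IgG and calcium in maintenance. It also conflicts with other text in the same SAP section.

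The counts assume that all 18 exchanges take place, that scheduled readings are present, that the FPE1 pre-exchange values serve as baseline, and that Appendix 8 governs sampling.

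The consequence is limited. No data are lost, the abnormal-value and maximal-shift summaries and the 72-hour adverse-event criterion are untouched, and all safety analysis is descriptive (SAP 9.1.5 and 9.2.3), so no test, endpoint or decision rule changes. This should be fixed, but it is not a condition for the trial's conclusions to stand.

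**What to change.** 1. In SAP section 7, restrict the last-value rule to repeat assessments at the same visit **and** the same scheduled time point: before, during or after for vital signs; pre- or post-exchange for laboratory tests.
2. In SAP 7.2.3 and 7.2.4, tabulate each scheduled time point separately, with change from baseline for each.
3. State that optional post-exchange values at LVPE visits are shown on their own rows, with their own number of patients, and are not pooled with pre-exchange values.

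The statement in SAP 7.2.4 that pre- and post-FPE values are not compared can remain; tables of within-session change would be a useful option but are not needed to cure the defect.

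The cost is a few sentences and some extra table rows. No new data are needed, and the efficacy analysis is unaffected.

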7.1 EFFICACY END POINT(S)

Primary Efficacy Variables

- *Change from baseline in the cognitive scores as measured by ADAS-Cog (6 measurements: weeks: -3, -2 or -1, and 7-8; months: 6, 9, 12 and 14), and*
- *Change from baseline in the ADCS-ADL 6 measurements: weeks: -3, -2 or -1, and 7-8; months: 6, 9, 12 and 14).*

	Title: Statistical Analysis Plan
	Project #: IG1002 AMBAR
	Version: Final 1.0 Effective Date: 31July2018
	Protocol Version: Version 5.0 Effective Date: Feb2018

Secondary Efficacy Variables

Change from baseline in the cognitive, functional and neuropsychiatric scores and overall development as measured by MMSE, NPS battery, NPI, CDR-Sb, ADCS-CGIC, CSDD, C-SSRS. (6 measurements: week: -3, -2 or -1, and 7-8; months: 6, 9, 12 and 14) and QoL-AD, RUD-Lite® (5 measurements: week: -3, -2 or -1; months: 6, 9, 12 and 14).

The set of FAS patients set will be used for all efficacy summaries unless otherwise noted. Summaries will be presented by treatment group unless otherwise noted. The 3 active treatment groups (half albumin, half albumin + IVIG, and full albumin+ IVIG) will also be pooled together and analyzed as combined active treatment group.

Details for each efficacy variable are presented below.

7.1.1 Alzheimer’s Disease Assessment Scale – Cognitive (ADAS-Cog)

[figure not shown]
The ADAS-Cog Scale is a questionnaire that assesses cognitive performance in 12 different domains. The domains (and the maximum score) are: (word recall (10), commands (5), constructional praxis (5), delayed word-recall task (10), naming objects/figures (5), ideation praxis (5), orientation (8), word recognition (12), remembering test instructions (5), comprehension (5), word finding difficulties (5), and spoken language ability (5). A total score can be derived by summing across all domains (0-80). Within each domain, and for the total, a higher score indicates more cognitive impairment.

The total score will be analyzed as continuous variables, and will be summarized at each time point.

The total ADAS-Cog score at 14 months is the end point for the primary efficacy analysis. The other point in time will be regarded as secondary end points.

